### **8.3.5.2. Exposure During Breastfeeding**

An EDB occurs if:

- A female participant is found to be breastfeeding while receiving or after discontinuing study intervention.
- A female is found to be breastfeeding while being exposed or having been exposed to study intervention (ie, environmental exposure). An example of environmental EDB is a female family member or healthcare provider who reports that she is breastfeeding after having been exposed to the study intervention by ingestion, inhalation, or skin contact.

The investigator must report EDB to Pfizer Safety within 24 hours of the investigator's awareness, irrespective of whether an SAE has occurred. The information must be reported using the CT SAE Report Form. When EDB occurs in the setting of environmental exposure, the exposure information does not pertain to the participant enrolled in the study, so the information is not recorded on a CRF. However, a copy of the completed CT SAE Report Form is maintained in the investigator site file.

An EDB report is not created when a Pfizer drug specifically approved for use in breastfeeding women (eg, vitamins) is administered in accord with authorized use. However, if the infant experiences an SAE associated with such a drug, the SAE is reported together with the EDB.

### **8.3.5.3. Occupational Exposure**

An occupational exposure occurs when a person receives unplanned direct contact with the study intervention, which may or may not lead to the occurrence of an AE. Such persons may include healthcare providers, family members, and other roles that are involved in the trial participant's care.

The investigator must report any instance of occupational exposure to Pfizer Safety within 24 hours of the investigator's awareness using the CT SAE Report Form, regardless of whether there is an associated SAE. Since the information about the occupational exposure does not pertain to a participant enrolled in the study, the information is not recorded on a CRF; however, a copy of the completed CT SAE Report Form must be maintained in the investigator site file.

### **8.3.6. Cardiovascular and Death Events**

Not Applicable.

### **8.3.7. Disease-Related Events and/or Disease-Related Outcomes Not Qualifying as AEs or SAEs**

Not applicable.

### **8.3.8. Adverse Events of Special Interest**

Injection site reactions will be considered an AESI. Injection site reactions may include but are not limited to erythema, induration, ecchymosis, pain and pruritis. The size and severity of these symptoms or reactions will be assessed and documented. The following details will be collected:

- Date of onset and resolution of the ISR;
- Presence of the following features on a mild/moderate/severe grading scale:
  - Erythema;
  - Induration;
  - Pain;
  - Swelling;
  - Pruritis.
- Did the ISR lead to any missed or delayed doses?
- Did the ISR lead to withdrawal of the participant from the study?

AESIs are examined as part of routine safety data review procedures throughout the clinical trial and as part of signal detection processes.

All AESIs must be reported as an AE or SAE following the procedures described in [Sections 8.3.1](#) through [8.3.4](#). An AESI is to be recorded as an AE or SAE on the CRF. In addition, an AESI that is also an SAE must be reported using the CT SAE Report Form.

### 8.3.8.1. Lack of Efficacy

The investigator must report signs, symptoms, and/or clinical sequelae resulting from lack of efficacy. Lack of efficacy or failure of expected pharmacological action is reportable to Pfizer Safety **only if associated with an SAE**.

### 8.3.9. Medical Device Deficiencies

Not Applicable.

### 8.3.10. Medication Errors

Medication errors may result from the administration or consumption of the study intervention by the wrong participant, or at the wrong time, or at the wrong dosage strength.

Exposures to the study intervention under study may occur in clinical trial settings, such as medication errors.

Safety Event	Recorded on the CRF	Reported on the CT SAE Report Form to Pfizer Safety Within 24 Hours of Awareness
Medication errors	All (regardless of whether associated with an AE)	Only if associated with an SAE

Medication errors include:

- Medication errors involving participant exposure to the study intervention;
- Potential medication errors or uses outside of what is foreseen in the protocol that do or do not involve the study participant;
- The administration of expired study intervention;
- The administration of an incorrect study intervention;
- The administration of an incorrect dosage;
- The administration of study intervention that has undergone temperature excursion from the specified storage range, unless it is determined by the sponsor that the study intervention under question is acceptable for use.

Such medication errors occurring to a study participant are to be captured on the medication error page of the CRF, which is a specific version of the AE page.

In the event of a medication dosing error, the sponsor should be notified within 24 hours.

Whether or not the medication error is accompanied by an AE, as determined by the investigator, the medication error is recorded on the medication error page of the CRF and, if applicable, any associated AE(s), serious and nonserious, are recorded on the AE page of the CRF.

Medication errors should be reported to Pfizer Safety within 24 hours on a CT SAE Report Form **only when associated with an SAE**.

#### **8.4. Pharmacokinetics**

Trough blood samples of approximately 2 mL, to provide a minimum of serum volume 1 mL, will be collected for measurement of serum concentrations of recifercept as specified in the [SoA](#) Instructions for the collection and handling of biological samples will be provided in the laboratory manual or by the sponsor. The actual date and time (24-hour clock time) of each sample will be recorded.

The actual times may change, but the number of samples will remain the same. All efforts will be made to obtain the samples at the exact nominal time relative to dosing.

Samples will be used to evaluate the population PK of recifercept. Each serum sample will be divided into 2 aliquots (1 each for Intact recifercept and Total [intact + clipped] recifercept analysis). Samples collected for analyses of recifercept serum concentration may also be used to evaluate safety or efficacy aspects related to concerns arising during or after the study, for metabolite identification and/or evaluation of the bioanalytical method, **CCI**

Genetic analyses will not be performed on these serum samples. Participant confidentiality will be maintained.

Samples collected for measurement of serum concentrations of recifercept will be analyzed using a validated analytical method in compliance with applicable SOPs.

The PK samples must be processed and shipped as indicated in the instructions provided to the investigator site to maintain sample integrity. Any deviations from the PK sample handling procedure (eg, sample collection and processing steps, interim storage or shipping conditions), including any actions taken, must be documented and reported to the sponsor. On a case-by-case basis, the sponsor may make a determination as to whether sample integrity has been compromised.

Any changes in the timing or addition of time points for any planned study assessments must be documented and approved by the relevant study team member and then archived in the sponsor and site study files but will not constitute a protocol amendment. The IRB/EC will be informed of any safety issues that require alteration of the safety monitoring scheme or amendment of the ICD.

CCI [REDACTED]

[REDACTED]

[REDACTED]

[REDACTED]

[REDACTED]

[REDACTED]

[REDACTED]

[REDACTED]

| [REDACTED]

| [REDACTED]

[REDACTED]

[REDACTED]

[REDACTED]

[REDACTED]

[REDACTED]

CCI [REDACTED]

[REDACTED]

[REDACTED]

[REDACTED]

[REDACTED]

[REDACTED]

[REDACTED]

[REDACTED]

[REDACTED]

[REDACTED]

[REDACTED]

[REDACTED]

[REDACTED]

[REDACTED]

CCI

### 8.7. Immunogenicity Assessments

Blood samples of approximately 2 mL, to provide a minimum of 1 mL serum volume, will be collected for determination of ADA and NAb as specified in the [SoA](#). Instructions for the collection and handling of biological samples will be provided in the laboratory manual or by the sponsor. The actual date and time (24-hour clock time) of each sample will be recorded.

Samples collected for determination of ADA and NAb may also be used for additional characterization of the immune response and/or evaluation of the bioanalytical method, CCI. These data will be used for internal exploratory purposes.

Genetic analyses will not be performed on these serum samples. Participant confidentiality will be maintained.

Samples will be analyzed using a validated analytical method in compliance with applicable SOPs. Samples determined to be positive for ADA may be further characterized for NAb.

The immunogenicity samples must be processed and shipped as indicated in the instructions provided to the investigator site to maintain sample integrity. Any deviations from the immunogenicity sample handling procedure (eg, sample collection and processing steps, interim storage, or shipping conditions), including any actions taken, must be documented and reported to the sponsor. On a case by case basis, the sponsor may make a determination as to whether sample integrity has been compromised.

Any changes in the timing or addition of time points for any planned study assessments must be documented and approved by the relevant study team member and then archived in the sponsor and site study files, but will not constitute a protocol amendment. The IRB/EC will be informed of any safety issues that require alteration of the safety monitoring scheme or amendment of the ICD.

CCI

## 9. STATISTICAL CONSIDERATIONS

Detailed methodology for summary and statistical analyses of the data collected in this study is outlined here and further detailed in a SAP, which will be maintained by the sponsor. The SAP may modify what is outlined in the protocol where appropriate; however, any major modifications of the primary endpoint definitions or their analyses will also be reflected in a protocol amendment.

## 9.1. Statistical Hypotheses

### 9.1.1. Estimands

Not applicable.

## 9.2. Analysis Sets

For purposes of analysis, the following analysis sets are defined:

Participant Analysis Set	Description
FAS/Safety	All participants receiving at least 1 dose of recifercept. Participants will be analyzed according to the dose they actually received.
PPAS	All participants receiving at least 1 dose of recifercept and have complete data at baseline through month 24 and without protocol deviations that were thought to impact the efficacy evaluation during the treatment period.  Participants will be analyzed according to their randomized dose.
PK Concentration set	All participants who received at least 1 dose of recifercept and have at least 1 evaluable concentration result.

## 9.3. Statistical Analyses

The SAP will be developed and finalized before any analyses are performed and will describe the analyses and procedures for accounting for baseline, missing, unused, and spurious data. This section is a summary of the planned statistical analyses of the primary and secondary endpoints.

### 9.3.1. General Considerations

Data presented in tables will be summarized by recifercept dose (defined in [Section 4.1](#)) and total. If needed summary presentations may also be grouped by gender.

### 9.3.2. Primary Endpoint(s)/Estimand(s) Analysis

#### *Efficacy*

The primary efficacy endpoint of change from baseline of height at 24 months will be analyzed using an ANOVA model comprising terms for recifercept dose groups. Change from baseline estimates for height and their corresponding 95% confidence intervals will be provided via least-square means. The population for the primary analysis will be based on the FAS.

### *Safety*

The safety data will be summarized in accordance with Pfizer Data Standards. All participants who receive IP (safety population) will be included in the safety analyses. All safety data will be summarized descriptively through appropriate data tabulations, descriptive statistics, categorical summaries, and graphical presentations. Safety endpoints for the study include:

- TEAEs and SAEs;
- Withdrawals from treatment due to AEs.

Change from baseline in laboratory data and vital signs will be additionally summarized. Participant listings will also be produced for these safety endpoints.

The primary efficacy estimand will be the population treatment effect of the mean change-from-baseline of a continuous response (ie, height, growth) at month 24 irrespective of IP compliance. Increase in height growth above expected growth in reference population, a co-primary endpoint, is defined as the height growth in the achondroplasia reference population +50%. Intercurrent event for the efficacy estimand: withdrawal and all events leading missing data will be excluded from efficacy analysis and will not have their data imputed. The population-based treatment effect will be the mean change-from-baseline at Month 24.

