### **Statistical Methods**

Detailed methodology for summary and statistical analyses of the data collected in this study is outlined here and further detailed in a SAP, which will be maintained by the sponsor. The SAP may modify what is outlined in the protocol where appropriate; however, any major modifications of the primary endpoint definitions or their analyses will also be reflected in a protocol amendment.

The primary efficacy estimand will be the population treatment effect of the mean change-from-baseline of a continuous response (ie, height, growth) at month 24 irrespective of IP compliance. Increase in height growth above expected growth in reference population, a co-primary endpoint, is defined as the height growth in the achondroplasia reference population +50%. Intercurrent event for the efficacy estimand: withdrawal and all events leading missing data will be excluded from efficacy analysis and will not have their data imputed. The population-based treatment effect will be the mean change-from-baseline at Month 24.

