## 3. OBJECTIVES, ENDPOINTS, AND ESTIMANDS

Objectives	Endpoints	Estimands
Primary:	Primary:	Primary:

 
• Evaluate the long-term safety and tolerability of recifercept doses and dosing regimes in participants aged <math>\geq 15</math>m to <math>\leq 12</math> years with achondroplasia.
 
	
 
• N/A.
 
	Long-term safety and tolerability of recifercept as assessed through frequency and severity of AEs/SAEs.

 
• To assess long-term efficacy of recifercept to increase height growth in children with achondroplasia.
 
	
 
• The primary efficacy estimand is intended to provide a population level estimate of the effect of the IP on a continuous endpoint.
 
• Population-level summary: ratio between participants in the trial and a reference population [Merker et al, 2018] in growth of height at 24 month; ratio between treated and reference population is observed change-from-baseline of treated participants standardized by reference participant given age and gender.
 
	
 
• Increase in height growth above expected in reference population [Merker et al, 2018].
 

Secondary:	Secondary:	Secondary:

 
• To evaluate the PK of recifercept in children aged <math>\geq 15</math>m to <math>\leq 12</math> years old with .
 
		
 
• Population PK characterization in children aged <math>\geq 15</math>m to <math>\leq 12</math> years old with achondroplasia. CL/F and other PK parameters of recifercept to assess exposures in different age group.
 

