1. INTRODUCTION

This statistical analysis plan (SAP) provides the detailed methodology for summary and statistical analyses of the data collected in Study C4181008. This document may modify the plans outlined in the protocol; however, any major modifications of the primary endpoint definition or its analysis will also be reflected in a protocol amendment.

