1.1.1. Primary Estimand(s)

The primary estimand is defined according to the primary objective and is in alignment with the primary endpoint. It includes the following 4 attributes:

- Population: Patients with achondroplasia, as defined by inclusion/exclusion criteria;
- Variable: Height Growth at 24 months;
- Height Growth = (Observed Change from Baseline (from study C4181005) in standing height (cm))/(Expected Change from Baseline (cm)[Merker et al, 2018]¹)

- Intercurrent event(s): Withdrawal and all events leading to missing data will be excluded from efficacy analysis and will not have their data imputed;
- Population-level summary: Mean Height growth at 24 months adjusted for age and gender.

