2. ENDPOINTS AND BASELINE VARIABLES: DEFINITIONS AND CONVENTIONS

2.1. Primary Endpoint(s)

Safety

Safety and tolerability of recifercept as assessed through frequency and severity of AEs/SAEs.

Efficacy

Increase in height growth above expected in reference population [Merker et al, 2018].

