4.1. Hypotheses and Decision Rules

There are no statistical hypotheses for this protocol.

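### The protocol defines the co-primary height endpoint both with and without a +50% benchmark, the SAP only without it, and the listed outputs do not place the growth ratio against either 1.0 or 1.5

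*Protocol*

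**What the plan says.** **With the 50%.** Protocol Section 9.3.2, in the block headed Safety, says that the co-primary measure of increased growth "is defined as the height growth in the achondroplasia reference population +50" per cent. The synopsis (Statistical Methods) carries the same sentence.

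**Without the 50%, in the protocol.** The objectives tables in Sections 1.1 and 3 give the endpoint as growth above expected in the reference cohort. The population-level summary there is a ratio: "ratio between treated and reference population is observed change-from-baseline of treated participants standardized by reference participant given age and gender". The Efficacy paragraph of Section 9.3.2 takes a third form, plain change in height: "The primary efficacy endpoint of change from baseline of height at 24 months will be analyzed using an ANOVA model comprising terms for recifercept dose".

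**Without the 50%, in the SAP.** SAP 2.1 gives the endpoint as "Increase in height growth above expected in reference population". SAP 1.1.1 and Appendix 2.2 define it as a continuous ratio of observed to expected change. The estimand's summary line reads "Population-level summary: Mean Height growth at 24 months adjusted for age and gender". No SAP statement of this endpoint contains +50% or 1.5.

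**Decision rule.** SAP 4.1 says "There are no statistical hypotheses for this protocol". Protocol 9.1 states none.

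**Outputs.** SAP 5.1.1.1 names change relative to the reference as the analysis variable. The descriptive statistics, LS means, dose differences and 95% confidence intervals it then lists are for standing height. The model code in Appendix 4 has a response called height, and Appendix 1 lists the endpoint as change in mean standing height.

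**The concern.** The study is open label and has no untreated arm, so comparison with the reference cohort is its only route to an efficacy statement about the drug. A plan with two versions of that comparison, and no account of how they relate, leaves the choice of benchmark open until results are known. Protocol 9.4 allows the sponsor to look at data during the study to support clinical development, which makes an unfixed benchmark more exposed.

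At stake is what may be said about a moderate effect. Growth of 20% or 30% over reference fits the objectives-table wording and falls short of the synopsis wording. If the reports then show only centimetres of standing height, the reader cannot see where the ratio lies against either value.

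**Working it through.** The documents give no sample-size, power or precision figure for this endpoint, so there is none to reproduce.

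**Step 1. Put +50% on the SAP's scale.** SAP Appendix 2.2 defines H = (observed change in height) / (expected change for age and gender). If observed change = expected change × (1 + 0.50), then H = 1.5. Growth equal to expected is H = 1.0. Both values are translations of wording; neither document writes them as cut-offs.

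**Step 2. Where the wordings part.**

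| Mean H | Above expected | At least +50% |
|---|---|---|
| 0.95, 1.00 | no | no |
| 1.10, 1.25, 1.49 | yes | no |
| 1.50, 1.60 | yes | yes |

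They disagree only for H above 1.0 and below 1.5.

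**Step 3. Is that gap large against the likely precision?** Assumptions: about 63 children (protocol) split equally over three doses, 63 / 3 = 21; SD of H of 0.2, 0.3 or 0.4, since the documents give no SD. Half-width = t(0.975, 20) × SD / √21, with t = 2.086 and √21 = 4.583.

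| SD of H | Half-width | 95% CI if mean H = 1.20 | 95% CI if mean H = 1.25 |
|---|---|---|---|
| 0.2 | 0.09 | 1.11 to 1.29 | 1.16 to 1.34 |
| 0.3 | 0.14 | 1.06 to 1.34 | 1.11 to 1.39 |
| 0.4 | 0.18 | 1.02 to 1.38 | 1.07 to 1.43 |

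Every interval lies wholly between 1.0 and 1.5. Fewer children would not quickly change this. At SD 0.4 and 13 children, the half-width is 2.179 × 0.4 / √13 = 0.24, still inside the 0.25 that separates 1.25 from each value. For all 63 children and SD from 0.2 to 0.5, it is 0.05 to 0.13.

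**Step 4. Does the role of +50% matter?** Take mean H = 1.25 and SD 0.3, and suppose H is normal. As a benchmark for the mean, 1.5 is not reached. As a per-child criterion, the share at or above 1.5 is P(Z ≥ (1.5 − 1.25) / 0.3) = P(Z ≥ 0.83) = 0.20, or 0.20 × 21 ≈ 4 children per dose. The two roles give different summaries, and the plan names neither.

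**Step 5. Can the listed outputs answer it?** The expected change in H's denominator depends on age and gender. A mean change in centimetres therefore corresponds to no single H, and standing-height LS means cannot be read against 1.0 or 1.5 unless H itself is reported.

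**The case against.** The strongest reply is that this is descriptive work with no hypotheses, so a loose benchmark harms nothing. Part of that stands. A reader might infer that a ratio between 1.0 and 1.5 is a success under one document and a failure under the other. The documents do not support this: no visible text attaches a test, an error rate or a decision to 1.0 or 1.5, and Appendix 2.2 defines H with no cut-off.

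A reader might also infer that the SAP dropped a protocol definition in breach of its own undertaking that "any major modifications of the primary endpoint definition or its analysis will also be reflected in a protocol amendment". That is not shown either. The SAP follows the protocol's objectives tables, so the conflict starts inside the protocol. It is true only that Amendment 1, which is country-specific, does not resolve it.

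Third, one could say that the endpoint is never evaluated. That goes too far. SAP 5.1.1.1 does name reference-relative change as the modelled variable, and height in the code may be a placeholder name. If H were reported with its interval, any reader could compare it with 1.0 or 1.5. The outputs listed, however, are for standing height. Some protocol text near the end of Section 9 is redacted, so only the visible text can be called silent.

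Finally, the +50% may be a per-child threshold, a target for the mean or a descriptive benchmark. That is a fair reading of the text, and it supports the point: the definition of a co-primary endpoint should not leave this open. Equal groups of 21 at Month 24 are also not assured, because doses can change and the full analysis set groups children by dose received.

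**Conclusion.** The point holds as an unresolved definition, not as opposing verdicts. The synopsis and Section 9.3.2 put the co-primary endpoint at reference growth +50% (H = 1.5). The protocol's objectives tables and all SAP statements of the endpoint omit it, and its role is stated nowhere. Between 1.0 and 1.5, a mean H could afterwards be described either way, and the listed outputs would not show H against either value.

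The range is wide compared with the plausible imprecision: half-widths of 0.09, 0.14 and 0.18 against a gap of 0.5. Those half-widths illustrate the scale and rest on the assumed SDs and 21 children per dose. The existence of two definitions does not depend on them. This should be corrected; it does not invalidate the design.

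**What to change.** 1. Decide what +50% is: the benchmark for the mean ratio, or a per-child criterion. State it identically in Protocol 1.1, 3 and 9.3.2 and in SAP 1.1.1, 2.1, 5.1.1 and Appendix 2.2. If it is no longer wanted, remove it by protocol amendment before the Month 24 analysis.
2. In SAP 5.1.1.1, report the Month 24 LS mean of H with its 95% CI for each dose and overall, set against 1.0 and, if +50% is kept, 1.5. Make H the response in the Appendix 4 code for this endpoint, and align the Appendix 1 entry.
3. Add the number of children with H of at least 1.5 only if +50% is a per-child criterion.

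Cost: SAP wording, one table row per dose plus one overall, and a short protocol amendment to align or remove the text. No new data or visits are needed.

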5. ANALYSES AND SUMMARIES

5.1. Primary Endpoint(s)

5.1.1. Increase in height growth above expected in reference population

5.1.1.1. Main Analysis

- Estimand strategy: Hypothetical ([Section 1.1.1](#)).
- Analysis set: FAS ([Section 3](#)).
- Analysis methodology: Change from baseline relative to Merker (2018) will be analyzed using MMRM including data from Months 3-24 with gender (and possibly age), and whether a subject has switched doses of recifercept as covariates, subject (and/or time) as a random effect and an unstructured covariance matrix ([Section 4.2.1](#)).
- Intercurrent events and missing data: Data after study drug discontinuation and rescue will be excluded; intermediate missing values will not be imputed.
- The sample size, mean, standard deviation, median, minimum, and maximum at the baseline and postbaseline visits for observed standing height and change from baseline will be presented for each treatment arm.
- The least-squares (LS) means, the 95% confidence interval for the LS means, the difference between the LS means for each pair of treatment groups, and the corresponding 95% confidence interval will be presented for change from baseline in standing height for all postbaseline visits.

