8. APPENDICES

Appendix 1. Summary of Efficacy Analyses

Endpoint	Analysis Type	Population	Data Inclusion and Rules for Handling Intercurrent Events and Missing Data	Analysis Model
Change from baseline to Month 24 in mean standing height	Summary	FAS	Separately for observed data and imputed data.	N/A
	Main analysis	FAS	All data collected will be included regardless of intercurrent events. Missing data will not be imputed.	MMRM with terms time,dose, gender & age
	Sensitivity/supplementary analysis	PPAS	All data collected will be included regardless of intercurrent events. Missing data will not be imputed.	MMRM with terms time,dose, gender & age
Change from baseline to Month 12 in mean arm span-height difference	Summary	FAS	Separately for observed data and imputed data.	N/A
	Main analysis	FAS	All data collected will be included regardless of intercurrent events. Missing data will be not be imputed.	MMRM with terms time,dose, gender & age
	Sensitivity/supplementary analysis	PPAS	All data collected will be included regardless of intercurrent events. Missing data will not be imputed.	MMRM with terms time,dose, gender & age

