Appendix 2.3. Definition of Protocol Deviations That Relate to Statistical Analyses/Populations

Appendix 3. Data Set Descriptions

Appendix 4. Statistical Methodology Details

Linear Interpolation

Linear interpolation will be employed to provide mean expected standing height values at 6 month interval for children > age 4. The SAS code is as follows:

```
proc expand data=mydata out=LinInterp;  
    convert exp_mean=linear / method=join;  
    id age;  
run;
```

MMRM

MMRM will be used for height growth and arm span-height difference. The SAS code is as follows:

```
proc mixed data=mydata;  
    class dose gender month;  
    model height = dose month gender age/s;  
    random int month / type=un sub=subject;  
    lsmean dose;  
run;
```

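### The primary efficacy variable is stated in two ways, raw height change and growth relative to the reference, and the protocol's raw version labels natural growth as a treatment effect

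*Protocol*

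**What the plan says.** Two definitions run side by side.

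**Raw height.** Protocol 9.3.2, under Efficacy, says: "The primary efficacy endpoint of change from baseline of height at 24 months will be analyzed using an ANOVA model". The model's only terms are the dose groups, and it yields least-squares means and 95% intervals for height. Later in 9.3.2, and again in the synopsis under Statistical Methods, comes the label: "The population-based treatment effect will be the mean change-from-baseline at Month 24". In SAP 5.1.1.1 the final bullet says that least-squares means, pairwise dose differences and their intervals "will be presented for change from baseline in standing height for all postbaseline visits". SAP Appendix 1 names the endpoint as "Change from baseline to Month 24 in mean standing height". The Appendix 4 code reads "model height = dose month gender age/s".

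**Growth relative to the reference.** The objectives tables (Protocol 1.1 and 3, SAP 1.1) define the summary as a ratio to growth in a published European achondroplasia cohort, by age and gender. SAP 1.1.1 defines Height Growth as observed change divided by expected change and gives "Population-level summary: Mean Height growth at 24 months adjusted for age and gender". SAP Appendix 2.2 calls this ratio H and names it the primary efficacy endpoint. The methodology bullet of SAP 5.1.1.1 fits an MMRM to change relative to the reference.

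**The target.** The paragraph of Protocol 9.3.2 that carries the treatment-effect label also says that growth above the reference, "a co-primary endpoint, is defined as the height growth in the achondroplasia reference population +50" per cent. On the H scale that is 1.5.

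**The concern.** Protocol 4.1 gives every participant one of three active doses, and Protocol 4.2 limits the trial to children who are still growing. With no untreated arm, only the reference cohort can separate drug effect from natural growth. An analysis of raw centimetres leaves the reference out, so its mean change is positive whether or not the drug works, and calling it a treatment effect invites a wrong reading.

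A programmer who follows Protocol 9.3.2, the last bullet of SAP 5.1.1.1 and Appendix 1 would deliver results in centimetres. One who follows SAP 1.1.1, Appendix 2.2 and the methodology bullet would deliver H. Both texts are in force, so in an open-label study the choice could be made after the data have been seen.

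**Working it through.** **Figures to reproduce.** There are none. The visible text gives no growth rate, SD, effect size or power.

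**Inputs from the documents.** About 63 participants on three doses (Protocol 4.1), 24 months, H (SAP Appendix 2.2), and the +50% definition (Protocol 9.3.2).

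**Assumptions.** Equal split, 63/3 = 21 per dose (also tried at 15); untreated growth of 3 to 6 cm/year; SD of the 24-month gain 1 to 3 cm; one common expected gain g within a group.

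**Step 1: what each variable estimates.** Let g be the expected 24-month reference gain and d the drug effect in cm.
- Raw change: D = g + d.
- Ratio: H = D/g = 1 + d/g.
- No effect (d = 0): D = g and H = 1.0.
- The +50% definition (d = 0.5g): D = 1.5g and H = 1.5.

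At baseline H would be 0/0. A mean change from baseline can therefore only be the numerator of H, in centimetres.

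**Step 2: raw change under no effect and at +50%.**

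| Untreated growth (cm/year) | D with no effect (cm) | D at +50% (cm) |
|---|---|---|
| 3 | 6 | 9 |
| 4 | 8 | 12 |
| 6 | 12 | 18 |

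A raw mean of 9 cm is H = 9/6 = 1.5 if g is 6 cm, but H = 9/12 = 0.75 if g is 12 cm. The raw figure cannot answer the question without g.

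**Step 3: expected intervals with no drug effect.** Raw: g ± t × SD/√n. Ratio: 1 ± t × SD/(g√n). The degrees of freedom are 3n − 3, so t is 2.00 at n = 21 and 2.02 at n = 15.
- g = 8, SD = 2, n = 21: 8 ± 2.00 × 0.436 = 7.13 to 8.87 cm; H 0.89 to 1.11.
- g = 6, SD = 3, n = 21 (interval nearest zero at this n): 6 ± 2.00 × 0.655 = 4.69 to 7.31 cm; H 0.78 to 1.22.
- g = 6, SD = 3, n = 15: 4.44 to 7.56 cm; H 0.74 to 1.26.

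In every scenario the raw interval lies far above zero, while the interval for H contains 1.0 and excludes 1.5.

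**Step 4: age imbalance under the protocol's ANOVA, which has dose terms only.** Assume uniform ages from 1.25 to 12 years.
- SD of age = 10.75/√12 = 3.10 years.
- SE of a difference between two group mean ages = 3.10 × √(2/21) = 0.96 years.
- If growth falls evenly from 6 to 3 cm/year over that range, the slope is 3/10.75 = 0.28 cm/year per year of age.
- Chance imbalance then moves a 24-month pairwise difference by up to about 2 × 0.28 × 0.96 × 1.96 ≈ 1 cm.

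For scale, a +50% effect is 0.5g, or 3 to 6 cm.

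**The case against.** The strongest reply is that the plan does specify the right variable. H is in every objectives table, is the SAP estimand and is derived in Appendix 2.2. SAP 5.1.1.1 models it and points to SAP 4.2.1, which derives least-squares means and 95% intervals at each visit. That stands. A reader might infer that the plan reports raw height alone and leaves the reference question without an estimate; the documents do not support that.

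Some of the raw wording also looks like drafting residue. The display bullet in SAP 5.1.1.1 recurs word for word in SAP 5.2.1.1, where the endpoint is arm span minus height. The Appendix 4 code is one template for both endpoints, so its response name is weak evidence of intent. This too stands, but it does not explain Protocol 9.3.2, where the raw endpoint, the ANOVA and the label are stated outright.

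A reader might also infer a false-positive finding. SAP 4.1 states no hypotheses, so a raw interval above zero triggers no decision. Pairwise dose differences largely cancel natural growth when ages are balanced, and the doses come from the parent study's assignment. Age imbalance matters mainly for the protocol's ANOVA: SAP 4.2.1, Appendix 1 and Appendix 4 include age, although SAP 5.1.1.1 says only that it may be included.

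Nor is H a new endpoint brought in without an amendment, because the ratio was already in the protocol's objectives. The move from ANOVA to MMRM is different. Protocol 9 and SAP 1 call for an amendment when the primary analysis changes in a major way, and Amendment 1 is country-specific only.

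Finally, it may be said that a ratio is read against 1.0 by construction. But SAP 4.2.1 asks for p-values without naming a null value. If one were produced for a mean of H against a default of zero, it would test for no growth at all.

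**Conclusion.** The point holds as a contradiction over the primary efficacy variable, within the protocol, within the SAP and between them. The protocol's stated analysis and label give a wrong effect measure: with no drug effect it would show about 6 to 12 cm at Month 24, against H of about 1.0. In addition, no analysis uses the +50% definition. The harm is a misleading estimate and interval, not an inflated formal error rate.

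The centimetre figures rest on the assumed growth rates, SDs and equal split. The conclusion needs only that expected untreated growth be large relative to its standard error. Baseline is a further uncertainty: SAP 1.1.1 takes change from the parent study, while SAP 2.4 uses the latest screening result relative to Day 1 for height. With the parent-study baseline, raw gain would cover more than 24 months and be larger still.

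**What to change.** - Name H as the single primary efficacy variable in Protocol 9.3.2 and the synopsis, the SAP 5.1.1.1 display bullets, the Appendix 1 endpoint column and the Appendix 4 code.
- Report the Month 24 least-squares mean of H with its 95% CI, by dose and overall, read against 1.0 (growth as in the reference) and 1.5 (the +50% definition). The code's LS means are by dose only, so it also needs the dose-by-visit term that SAP 4.2.1 already specifies.
- Keep raw standing height and its change as descriptive tables, and stop calling the raw mean change a treatment effect.
- State in SAP 5.1.1.1 whether age is in the model.
- Replace the protocol's ANOVA with the SAP's MMRM through a protocol amendment.

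The cost is SAP wording, small edits to the code and a short amendment. No new data or visits are needed.
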